4.7.3. Secondary Efficacy Endpoints

All secondary endpoints will also be summarized using descriptive statistics. For the endpoints of MDS-UPDRS Part IA, Part IB, Part I total, Part II total, Part III total, and Part III subscores, CGI-I, and PGI-C the information collected after symptomatic PD treatment will be handled as in the primary analysis. The analysis of all other endpoints will include all the information available regardless of start of symptomatic PD treatment.

Change from baseline in MDS-UPDRS sub-scores: Part IA, Part IB, Part I total, Part II total, Part III total, and Part III subscores.

Results from the MDS-UPDRS sub-scores Parts IA, Part IB, Part I total, Part II total, and Part III total will be analyzed using the same approach as for the primary endpoint (Section 4.7.2). Cumulative distribution plots will also be presented.

For participants that started symptomatic PD treatment (as described in Section 4.3) the analysis of Part III total will be performed in both the “On” and the practically defined “Off” state (as described in Section 4.3.5).

Change from baseline in DaT-SPECT in ipsilateral (to the clinically dominant side) putamen binding ratio values

DaT-SPECT is a dopamine transporter SPECT imaging that uses a radioactive agent called ¹²³I-ioflupane to show the distribution of the dopamine transporters in the striatum. Among other indications, ¹²³I-ioflupane imaging is used for assessment of disease severity and progression. The change (between baseline and Week 52) in DaT-SPECT uptake values in the ipsilateral putamen to the most clinical affected side, will be analyzed via an analysis of covariance (ANCOVA), regardless of intake of symptomatic PD therapy during the first 52 weeks. The model will include the baseline value of the respective DaT binding ratio as a covariate and the covariates described in Section 4.7.1 as main effects. All data, regardless of whether the participant has started symptomatic PD therapy will be included. There will be no imputation for missing values.

Change from baseline in Montreal Cognitive Assessment (MoCA) total score from baseline at week 24 and week 52.

The Montreal Cognitive Assessment (MoCA) was developed as a tool to screen patients who present with mild cognitive complaints and usually perform in the normal range on the MMSE. The change (between baseline and Week 52) in MoCA total score will be analyzed via an analysis of covariance (ANCOVA). The model will include the covariates described in Section 4.7.1 as main effects. All data, regardless of whether the participant has started PD symptomatic therapy will be included. The same model will be applied to the change from baseline at week 24.

Change from baseline Clinical Global Impression of Improvement Scales

The CGI-S is a measure of disease severity at baseline and is rated on a 7-point scale, with the severity (CGI-S) of illness scale using a range of responses from 1 (normal, not at all ill) through to 7 (amongst the most extremely ill patients). The CGI-S is only measured at baseline and will be described descriptively.

The CGI-I is intended as a measure of change in health status. CGI-I scores range from 1 (very much improved) through to 7 (very much worse).

For the CGI-I, patients will be divided into one of two groups:

- 'Responders': Score of 1-4 (i.e., rated as "no change", "minimally improved", "much improved" or "very much improved").
- 'Progressors': Score of 5-7 (i.e., rated as "minimally worse", "much worse" or "very much worse").

The proportion of patients rated by CGI-I Scale grouping at week 24 and week 52 will be analyzed using a logistic regression model, including all appropriate covariates described in Section 4.7.1. The estimated odds ratio for 'responders' and 'progressors' at week 24 and week 52 for treated patients compared to placebo will be presented with 80% CI.

Change from baseline in Patient Global Impression of Change (PGIC)

The Patient Global Impression of Change (PGIC) is intended as a measure of change in health state from the patient's perspective. PGIC scores range from 1 (very much improved) through to 7 (very much worse). Analysis of the PGI-C will follow the same methodology outlined for the CGI-I, above.

Change from baseline in Schwab and England Activities of Daily Living (SE-ADL) from baseline at week 52

The SE-ADL is a score when the participant selects the rating that most accurately describes their level of functional independence. The change (between baseline and Week 52) in SE-ADL score will be analyzed via an analysis of covariance (ANCOVA). The model will include the covariates described in Section 4.7.1 as main effects. All data, regardless of whether the patient has started PD symptomatic therapy will be included. The same model will be applied to the change from baseline at week 24.

Time to worsening of motor or non-motor symptoms as measured by MDS-UPDRS .

This endpoint is defined as the time to between first dose of study medication and the date when the patient increase in MDS-UPDRS Part I of 3 or more points, or in MDS-UPDRS Part II of 3 or more points, whatever come first.

The time to the composite event will be plotted using a Kaplan-Meier survival plot, and it will be analyzed via a Cox proportional hazards model to obtain a treatment difference between each of the prasinezumab dose levels against placebo; the covariates described in Section 4.7.1 will be included in the model. The time to the individual component of the composite event will be analyzed as indicated above by the composite event. If the assumption of proportional hazards is violated then a generalized Wilcoxon test will be undertaken to compare the survival curves. All data regardless of symptomatic PD treatment will be taken into consideration.

Time to start of dopaminergic (levodopa or dopamine agonist) treatment.

This endpoint is defined as the time to between first dose of study medication and the date when the patient starts dopaminergic treatment (as defined in Section 4.3.2). It will be plotted using a Kaplan-Meier survival plot, and will be analyzed via a Cox proportional

hazards. If the assumption of proportional hazards is violated then a generalized Wilcoxon test will be undertaken to compare the survival curves.

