## **6.6.2            Secondary Efficacy Endpoints**

For the endpoints of MDS-UPDRS Part IA, Part IB, Part I total, Part II total, Part III total, and Part III subscores, CGI-I, and PGI-C the information collected after symptomatic PD treatment or after an increase in MAO-B inhibitor therapy will be handled as in the primary analysis. The analysis of all other secondary endpoints will include all the information available regardless of start of symptomatic PD treatment.

An important biomarker secondary endpoint is the change (between baseline and the Week 52 visit) in DaT-SPECT uptake values in the ipsilateral putamen, which will be analyzed via an analysis of covariance (ANCOVA), regardless of intake of symptomatic PD therapy during the first 52 weeks. The model will include the covariates described in Section 6.6 as main effects. There will be no imputation for missing values.

Other secondary endpoints, which will also be analyzed at the end of Part 1 (after 52 weeks of treatment with either placebo or active treatment) include:

- Change in MDS-UPDRS sub-scores from baseline to Week 52 for Part IA, Part IB, Part I total, Part II total, Part III total, and Part III subscores (bradykinesia, resting tremor and axial symptoms) analyzed with exactly the same MMRM approach as for the primary endpoint.
- Change in MoCA total score from baseline to Week 52 analyzed with an analysis of covariance (ANCOVA).

- CGI-I will be analyzed using a logistic regression model, including the covariates described in Section 6.6.
- PGI-C will be analyzed using a logistic regression model, including the covariates described in Section 6.6.
- Change in Schwab and England Activities of Daily Living (SE-ADL) from baseline to Week 52 will be analyzed with ANCOVA.
- Time to first occurrence of either of the following:  $\geq 3$  points change from baseline in MDS-UPDRS Part I, or  $\geq 3$  points change from baseline in MDS-UPDRS Part II will be analyzed with a Cox proportional hazards model including the covariates described in Section 6.6, along with a Kaplan-Meier plot.
- Time to start of dopaminergic (levodopa or dopamine agonists) treatment will be analyzed with a Cox proportional hazards model including the covariates described in Section 6.6, along with a Kaplan-Meier plot. Events in this analysis will only consider the start of levodopa or dopamine agonist.

All secondary endpoints will also be summarized using descriptive statistics.

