4.6. TIME WINDOWS

The analysis of data will be undertaken using time windows. As all the endpoints in the study are collected at different time frequencies, three different set of time windows will be applied depending on the endpoint. The analysis of all the endpoints collected every four weeks will be undertaken using the time windows described in Table 3. For the scales and questionnaires collected every eight weeks or more, Modified Hoehn & Yahr, MDS-UPDRS, CGI-I, PGI-C, MoCA, PDQ-39, SCOPA-AUT, SE-ADL, and PDSS-2, the time windows that will be used in the analysis are described in Table 4. All the endpoints collected with the remote device will be analysed with the windows described in Table 5.

The reporting windows will be applied to every single data point obtained for analyses regardless of the visit label used to collect the data, i.e. scheduled, unscheduled, or prior to start symptomatic treatment visits. If there are two or more visits mapped to exactly the same reporting window, then the following rules will be used to apply the data analysis flag to the assessment, i.e. the data flag used for the by visits reported as described in this SAP:

1. If neither of the visits are labelled as “Prior to start dopaminergic treatment visit” (as per protocol), flag the data from the last available visit.
2. If any visit is labelled as “Prior to start dopaminergic treatment visit” (as per protocol), then flag the data from this visit in the analysis.

Table 3. Windows for assessments collected every four weeks (vitals, physical examination, C-SSRS, ECG, ADAs, hematology, etc).

	Scheduled Week	Scheduled Day	Reporting window		
Part 1	1	1	≤ 1		
	1	2	2	to	4
	1	7	5	to	10
	2	14	11	to	20
	4	28	21	to	41
	8	56	42	to	69
	12	84	70	to	97
	16	112	98	to	125
	20	140	126	to	153
	24	168	154	to	181
	28	196	182	to	209
	32	224	210	to	237
	36	252	238	to	265
	40	280	266	to	293
	44	308	294	to	321
48	336	322	to	349	
52	364	350	to	Day before re-randomization to Part 2	

Table 4. Windows for assessments collected every 8 weeks or more

	Scheduled Week	Scheduled Day	Reporting window		
Part 1	1	1	≤ 1		
	8	56	2	to	83
	16	112	84	to	139
	24	168	140	to	195
	32	224	196	to	251
	40	280	252	to	307
	48	336	308	to	349
	52	364	350	to	Day before re-randomization to Part 2

Table 5. Windows for assessments collected in the remote device

	Scheduled Week	Scheduled Day	Reporting window		
Part 1	1	1	≤ 1		
	2	14	2	to	20
	4	28	21	to	34
	6	42	35	to	48
	8	56	49	to	62
	10	70	63	to	76
	12	84	77	to	90

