4.7.1. Covariate Adjustment

Unless otherwise noted, analyses of efficacy endpoints (primary, secondary, and exploratory) will include the following covariates in the model:

- Treatment: placebo, prasinezumab high dose (4500 mg and 3500 mg) and prasinezumab low dose (1500 mg).
- Background therapy at baseline (MAO-B inhibitor treatment): Yes or No.
- Age group: < 60 years vs \geq 60 years.
- Sex: male or female.
- DaT-SPECT contralateral (to the clinically most affected side) putamen binding ratio at baseline.

For each continuous endpoint the baseline of the endpoint will also be included in the model

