4.10. MISSING DATA

For the primary endpoint, the secondary endpoints of MDS-UPDRS Part III , CGI-I, and PGI-C, and all the exploratory PRO endpoints, assessments performed while on any symptomatic PD treatment started after randomization or after an increase in symptomatic PD treatment will not be included in the analysis. For the MDS-UPDRS missing values will be handled via the MMRM methodology. Missing items values for MDS-UPDRS are dealt with as described in section 4.7.2.1.

Data with missing visit and/or scheduled timepoint information (if relevant) will not be included in summary tables summarized by visit (and scheduled timepoint if relevant).

Missing data for PROs will be treated in line with license holder manuals

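### The Week 52 ANCOVAs for MoCA and SE-ADL make no use of Week 24 scores from participants who miss Week 52; one two-visit MMRM per scale would cost little and add mainly robustness

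*SAP*

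**What the plan says.** SAP 4.7.3 gives the MoCA analysis as "The change (between baseline and Week 52) in MoCA total score will be analyzed via an analysis of covariance (ANCOVA" and then adds: "The same model will be applied to the change from baseline at week 24". The SE-ADL paragraph has the same structure: "The change (between baseline and Week 52) in SE-ADL score will be analyzed via an analysis of covariance (ANCOVA", again followed by a Week 24 run. Protocol 6.6.2 agrees on the method: "Change in MoCA total score from baseline to Week 52 analyzed with an analysis of covariance (ANCOVA".

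The covariates in SAP 4.7.1 are treatment, MAO-B inhibitor use, age group, sex and baseline DaT-SPECT, and "For each continuous endpoint the baseline of the endpoint will also be included in the model". No Week 24 score enters the Week 52 model.

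Scores after the start of symptomatic treatment are kept. For MoCA: "All data, regardless of whether the participant has started PD symptomatic therapy will be included". The SE-ADL paragraph says the same. A missing Week 52 score therefore comes from withdrawal or a missed assessment.

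SAP 4.10 gives a model-based rule for one scale only: "For the MDS-UPDRS missing values will be handled via the MMRM methodology". The statement that nothing is imputed, in SAP 4.7.3, belongs to DaT-SPECT. The only MoCA sensitivity analysis (SAP 4.7.4) restricts to patients without symptomatic treatment, and SE-ADL has none.

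Scores are placed in visits by date (SAP 4.6): "The reporting windows will be applied to every single data point obtained for analyses regardless of the visit label used to collect the data". In SAP Table 4 the Week 24 window is Days 140 to 195, and the Week 52 window starts at Day 350.

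**The concern.** Two secondary endpoints are each analysed at two post-baseline visits by two unconnected models. A participant seen at Week 24 but not at Week 52 counts in the Week 24 result and adds nothing to the Week 52 result. For the primary endpoint, SAP 4.7.2.2 itself notes that correlated visits let dropouts contribute to the final time point. MoCA and SE-ADL do not get that benefit, and no reason is given.

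Two things are at stake. One is some precision. The other is bias in the Week 52 contrast if participants doing worse at Week 24 leave more often in one arm than in another. SAP Section 1 says that these analyses inform the Phase 3 design.

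**Working it through.** **Inputs**

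- 100 per arm, two-sided alpha 20%, so z = 1.2816 (SAP 2.4).
- Between-visit correlation ρ = 0.55 (SAP 2.4, given for MDS-UPDRS); range 0.3 to 0.8.
- Missing at Week 24: 5% (SAP Table 1, MDS-UPDRS).
- Missing at Week 52: 15% (SAP 2.4, DaT-SPECT); range 10 to 15%.
- Illustrative effect of 0.318 SD (Protocol 6.1, DaT-SPECT).

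The documents give no SD, effect, correlation or missing rate for MoCA or SE-ADL, so the last four inputs are assumptions. The Appendix 1 rows for these scales could not be read in the text available, so the visits are taken from SAP 4.7.3.

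**Step 1: the plan's own figure.** No power is stated for MoCA or SE-ADL. The nearest figure is the approximately 80% for the primary endpoint. A seven-visit MMRM with the SAP Table 1 SDs and missingness and ρ = 0.55 has SE 1.374, so power = Φ(3/1.374 − 1.2816) = 81.6%, which agrees. A completers-only comparison at Week 52 has SE = 9 × √(1/75 + 1/80) = 1.447 and power 78.6%.

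**Step 2: precision for MoCA and SE-ADL.** For two visits with monotone missingness and observed proportions p24 and p52:

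Var(MMRM) / Var(ANCOVA) = 1 − ρ² × (1 − p52/p24)

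At the central values: 1 − 0.3025 × (1 − 0.85/0.95) = 0.968. The SE ratio is √0.968 = 0.984, a fall of 1.6%. Effective n per arm rises from 85.0 to 85/0.968 = 87.8. With power = Φ(0.318/√(2/n) − 1.2816), power rises from 78.6% to 79.5%.

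| Missing at Week 52 | Fall in SE, ρ = 0.3 | ρ = 0.55 | ρ = 0.8 |
|---|---|---|---|
| 10% | 0.2% | 0.8% | 1.7% |
| 15% | 0.5% | 1.6% | 3.4% |

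**Step 3: bias.** 4,000 simulated trials per scenario, two arms of 100, residual SD 1, higher scores better, 5% missing at random at Week 24 and about 15% missing at Week 52. Where dropout depends on the Week 24 score, the log-odds of missing Week 52 rise by 1 per SD of worse score. Each cell covers a true effect of 0 and of 0.318.

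| Dropout by Week 52 | ANCOVA bias (SD), ρ = 0.55 | ρ = 0.8 |
|---|---|---|
| Completely random | −0.001 | 0.003 to 0.006 |
| Depends on Week 24, same in both arms | 0.000 to −0.006 | 0.001 to −0.011 |
| Depends on Week 24, placebo only | −0.054 to −0.056 | −0.078 to −0.081 |
| Opposite dependence in the two arms | −0.109 to −0.120 | −0.160 to −0.169 |

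The MMRM bias was at most 0.006 in every scenario. The Monte Carlo error of each entry is about 0.153/√4000 = 0.0024.

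For scale, the SE of the contrast at 85 per arm is √(2/85) = 0.153. Under no effect, a bias of 0.056 is a shift of 0.36 SE, and the two-sided error becomes Φ(−1.28 + 0.36) + Φ(−1.28 − 0.36) ≈ 0.179 + 0.050 = 23% instead of 20%. A bias of 0.078 gives about 26%. The sign here is against the drug because the worse placebo participants are lost; the same mechanism in an active arm would flatter it.

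**The case against.** The best case for leaving the plan alone has five parts.

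- **No inconsistency.** The protocol and the SAP agree on a pre-specified ANCOVA, which is a standard single-time-point analysis. This stands. A reader might infer that the SAP contradicts itself by using MMRM elsewhere. It does not: the primary MMRM has seven visits, excludes data after symptomatic treatment, implements a hypothetical strategy, and faces 20 to 25% planned missingness.
- **The gain in precision is negligible.** This largely stands. In simulation, when dropout depended on Week 24 in the same way in both arms and ρ was 0.55, the SE ratio was about 1.00, so no gain was visible.
- **The inputs may be too high.** The 15% for DaT-SPECT includes invalid scans, which have no counterpart here, and the primary endpoint's 20 to 25% counts starters of symptomatic treatment, whose MoCA and SE-ADL data are kept. SE-ADL is one item in 10% steps, and its correlation may differ from 0.55. This stands, hence the range down to 10% missing and ρ = 0.3.
- **Bias needs arm-dependent dropout.** A reader might infer that any dropout related to the Week 24 score biases the ANCOVA contrast. Step 3 does not support that: with the same dependence in both arms the bias is 0 to about 0.01 SD. Nothing in the documents shows that dropout will differ by arm in this way. It is only plausible: Protocol 5.2.1 says infusion reactions tend to be dose-related, and Table 1 takes patients with Grade 4 reactions off the study.
- **The MMRM is no complete cure.** It does not address missing-not-at-random dropout. Early-termination scores dated Day 196 to 349 fall in the Week 32 to 48 windows and would stay unused. This stands.

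None of this is a reason to prefer the ANCOVA. The MMRM uses more of the data already collected and needs a weaker condition than missingness explained by baseline covariates alone.

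**Conclusion.** The point holds as a low-cost improvement, not as a flaw that invalidates either endpoint. Complete-case analysis is implied by the lack of any rule for these scales; it is not stated. Week 24 scores are not thrown away, since they count in the Week 24 ANCOVA, but those of participants who miss Week 52 do not reach the Week 52 contrast.

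Precision alone would hardly justify the change: 0.2 to 3.4% in SE over correlation 0.3 to 0.8 and 10 to 15% missing. The case rests on protection against a bias of about 0.05 to 0.08 SD, or 17 to 26% of an illustrative 0.318 SD effect (0.054/0.318 and 0.081/0.318), if dropout depends on the Week 24 score in one arm only. That protection assumes data missing at random given the Week 24 score and the covariates.

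**What to change.** In SAP 4.7.3, replace the two MoCA ANCOVAs by one MMRM on the changes at Week 24 and Week 52, and do the same for SE-ADL. Specify:

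- the Section 4.7.1 covariates, with treatment-by-visit and baseline-by-visit terms;
- an unstructured 2×2 covariance and Kenward-Roger degrees of freedom;
- the Week 52 contrast as the secondary result, with Week 24 read from the same model;
- all data included regardless of symptomatic treatment, so that the estimand is unchanged;
- the present Week 52 ANCOVA kept as a sensitivity analysis.

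Add a line to SAP 4.10 naming this as the missing-data approach for both scales. SAP 4.7.5 reruns an endpoint's main model within subgroups, so the MoCA subgroup results would follow the new model.

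The cost is SAP wording and minor programming, with no new data. SAP Section 1 states that the SAP supersedes the protocol's analysis plan, so the change can be made there; it should be in place before the sponsor is unblinded to Part 1. The price is reliance on missing at random given the Week 24 score, which the text should state together with the limits on missing-not-at-random dropout and on scores in the Week 32 to 48 windows.

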4.7.4. Sensitivity Analyses

The analysis for the primary efficacy endpoint will be repeated to also include data from assessments performed while on any symptomatic PD treatment started after randomization. These assessments will only be included in the analysis if performed in a practically defined OFF state, see section 4.3.5. A descriptive analysis of the OFF state data will also be reported using descriptive statistics.

The primary endpoint will be re-analysed by only including patients who completed Part 1 without starting symptomatic PD treatment.

The MoCA score will be analysed considering patients without symptomatic PD treatment.

The primary endpoint of MDS-UPDRS total score (sum of Parts I, II, and III) will be analysed by calculating for each patient the baseline value as the average of pre-treatment values of the MDS-UPDRS total score (sum of Parts I, II, and III), i.e. the average of screening and Day 1. The same MMRM model described in Section 4.7.2 will be used.

For the CGI-I and PGIC scores the analysis censors patients with symptomatic PD treatment prior to week 52. To enable use of all available data, two sensitivity analyses will be performed for each score:

- Patients who initiate symptomatic PD treatment prior to the analysis time point will be considered to be 'progressors' regardless of their CGI-I or PGIC score.
- Patients' CGI-I or PGIC scores will be used to classify patients regardless of whether or not they initiated symptomatic PD treatment.

4.7.5. Subgroup Analyses

A subgroup analysis will be performed if there are at least 20% of patients from the mITT population in the subgroup at baseline. The model used for the main analysis of the endpoint will be run in each subgroup; the model will exclude the subgroup being analyzed if that was a covariate (e.g. MAO-B Inhibitors at baseline (yes vs. no)). The estimated treatment effects (prasinezumab vs. placebo) and corresponding 80% CIs from the models will be displayed graphically in a forest plot for each prasinezumab dose level and each level of the subgroups specified.

The following subgroup analyses will be undertaken for the primary endpoint, change from baseline in total MDS-UPDRS (sum of Parts I, II and III) at Week 52. The subgroup analyses will also be undertaken in the following endpoints: MDS-UPDRS Part II, MDS-

UPDRS Part III, Part III subscores, and MDS-UPDRS sums of Part II and III, DaT-SPECT, digital PASADENA motor score, MoCA score and the composite time to event:

- MAO-B Inhibitors at baseline (yes vs. no)
- Hoehn & Yahr stage at baseline (1 vs. 2)
- REM Sleep Behavior Disorder Screening Questionnaire (RBDSQ) at baseline (RBDSQ ≥ 5 vs. < 5)
- Data-Driven sub-phenotypes (Diffuse malignant vs. mild motor-predominant vs. intermediate) at baseline
- Alpha-Synuclein Skin (positive vs. negative) (staining by immunohistochemistry on skin biopsy sections at baseline)
- DaT-SPECT ipsilateral putamen very abnormal vs. abnormal (defined on the baseline data with a validated cutoff of 0.6)

For the derivations of the data-driven sub-phenotypes, scales are classified into motor and non-motor. The motor scales are UPDRS-Part II (Motor symptoms) and UPDRS-Part III (Motor signs). The non-motor scales are SCOPA-AUT, RBDSQ and MOCA. After each one of the scales have been divided into percentiles, the data-driven sub-phenotypes are defined as follows:

- *Diffuse malignant* - Either motor score greater than the 75th percentile AND at least 1 non-motor score greater than the 75th percentile OR all 3 non-motor scores greater than the 75th percentile
- *Mild motor-predominant* - Motor and all non-motor scores less than the 75th percentile
- *Intermediate* - All those individuals not meeting criteria for other subtypes

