### **Mini Mental State Examination (MMSE) (In-clinic)**

The Mini Mental State Examination (MMSE) consists of a set of standardized questions to assess a participant's mental status and identify the individual's general level of impairment. The questions target five areas; orientation, short term memory retention, attention, short term recall and language. This will be used as an inclusion criterion, to ensure that the patient is not cognitively impaired.

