### **The Montreal Cognitive Assessment (MoCA) (In-clinic)**

In early Parkinson's disease, patients usually perform in the normal range on the widely used MMSE. The Montreal Cognitive Assessment (MoCA) is a rapid screening instrument like the MMSE but was developed to be more sensitive to patients presenting with mild cognitive complaints. It briefly assesses short term and working memory, visuospatial abilities, executive function, attention, concentration, language and orientation ([Nasreddine et al 2005](#)).

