### **Scales for Outcomes in Parkinson’s Disease Assessment of Autonomic Dysfunction (SCOPA-AUT) (In-clinic)**

The Scales for Outcomes in Parkinson’s disease assessment of autonomic dysfunction (SCOPA-AUT) is a 25-item self-administered test developed to evaluate autonomic symptoms, such as gastrointestinal and urinary problems, in patients with PD (Visser et al 2004). Region scores of: gastrointestinal (seven items); urinary (six items); cardiovascular (three items); thermoregulatory (four items); pupillomotor (one item); and sexual (two items for men and two for women) problems can also be derived. Higher scores reflect worse autonomic functioning.

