  - Data-driven sub-phenotypes (diffuse malignant vs. mild motor-predominant vs. intermediate)

For the derivations of the data-driven sub-phenotypes, scales are classified into motor and non-motor. The motor scales are UPDRS-Part II (Motor symptoms) and UPDRS-Part III (Motor signs). The non-motor scales are SCOPA-AUT, RBDSQ and MOCA. After each one of the scales have been divided into percentiles, the data-driven sub-phenotypes are defined as follows:

- Diffuse malignant: either motor score greater than the 75th percentile AND at least 1 non-motor score greater than the 75th percentile OR all 3 non-motor scores greater than the 75th percentile
- Mild motor-predominant: Motor and all non-motor scores less than the 75th percentile
- Intermediate: All those individuals not meeting criteria for other subtypes

*The efficacy analyses will include all enrolled patients and will be presented separately for Part 1, Part 2, and Part 3 of the study. All additional statistical details for the efficacy analyses will be documented in the Statistical Analysis Plan (SAP).*

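### The sub-phenotype rule counts a high MoCA as severe, so good cognition helps make a patient diffuse malignant and poor cognition can pass as mild

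*SAP*

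**What the plan says.** SAP 4.7.5 builds the sub-phenotypes from two motor scales (MDS-UPDRS Parts II and III) and three others: "The non-motor scales are SCOPA-AUT, RBDSQ and MOCA". The derivation opens with "After each one of the scales have been divided into percentiles, the data-driven sub-phenotypes are defined as follows". Three classes follow:

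- **Diffuse malignant:** "Either motor score greater than the 75th percentile AND at least 1 non-motor score greater than the 75th percentile", or else all three non-motor scores above that cut.
- **Mild motor-predominant:** every motor and non-motor score lies under its 75th percentile.
- **Intermediate:** everyone else.

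Protocol 6.6 has the same rule ("either motor score greater than the 75th percentile AND at least 1 non-motor score greater than the 75th percentile"). Neither text reverses a scale, uses a 25th percentile, or says that percentiles run in order of severity.

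On direction, protocol 4.6.1.10 says of SCOPA-AUT: "Higher scores reflect worse autonomic functioning". For MoCA, protocol 4.6.1.9 says: "The Montreal Cognitive Assessment (MoCA) is a rapid screening instrument like the MMSE". An MMSE of 25 or less is exclusion criterion 5 (protocol 4.2.3), and the purpose of the MMSE is given as "This will be used as an inclusion criterion, to ensure that the patient is not cognitively impaired". The only other MoCA subgroup, in SAP Appendix 1, splits the raw total into lower (<22) and higher (>22).

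**The concern.** A single direction is applied to scales that point in opposite directions. On the MMSE, low means impaired. MoCA is presented as a test of the same kind, so a MoCA above its 75th percentile marks the best cognition in the trial. The rule books that as a severe non-motor feature.

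The subgroup sits in the main body of the SAP. It is run for each dose on the primary endpoint, MDS-UPDRS Part II, Part III, the Part III subscores, the sum of Parts II and III, DaT-SPECT, the digital motor score, MoCA and the composite time-to-event endpoint. SAP section 1 says the main-body analyses feed the study report and decisions on the Phase 3 design. A sub-phenotype that looks promising or unpromising on the forest plot would not be the one named on its label.

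**Working it through.** The documents give no figure for this rule, so there is none to reproduce. The check applies the rule as written, then again with MoCA reversed (below its 25th percentile = severe), and compares the classes.

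**What follows from the text alone**

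- A MoCA above the 75th percentile bars a patient from mild.
- A low MoCA always satisfies the MoCA part of mild.
- A high MoCA plus one high motor score is enough for diffuse malignant.
- The route through all three non-motor scales needs bad autonomic and sleep scores together with excellent cognition.

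**Exact result if the five scales are independent and continuous**

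Inputs: each scale exceeds its cut with p = 0.25. RBDSQ is taken as higher = worse, which the documents do not state.

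- At least one motor score high: m = 1 − 0.75² = 0.4375.
- At least one of three non-motor scores high: q = 1 − 0.75³ = 0.5781.
- Diffuse malignant: m·q + p³ − m·p³ = 0.2529 + 0.0156 − 0.0068 = 0.2617.
- Mild: 0.75⁵ = 0.2373. Intermediate: 1 − 0.2617 − 0.2373 = 0.5010.

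Under independence the reversal leaves these sizes unchanged, but the membership changes. Only the best and worst cognitive quarters are affected. Within each, switching the MoCA flag changes the class for three patterns of the other four scales:

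- Motor high, SCOPA-AUT and RBDSQ both not high (diffuse malignant or intermediate): 0.4375 × 0.5625 = 0.2461.
- Motor not high, SCOPA-AUT and RBDSQ both high (diffuse malignant or intermediate): 0.5625 × 0.0625 = 0.0352.
- None of the four high (intermediate or mild): 0.75⁴ = 0.3164.

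The sum is 0.5977. Half the patients are in those two quarters, so 0.5 × 0.5977 = **29.9%** change class. For the 316 participants mentioned in protocol 1.3.2, that is about 94.

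The same terms give:

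- Labelled diffuse malignant but not so when reversed: 0.25 × (0.2461 + 0.0352) / 0.2617 = 26.9%. By symmetry the same share of the correctly defined group is missed.
- Labelled mild but in the worst cognitive quarter: 0.25 × 0.3164 / 0.2373 = 33.3%.

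**With correlation between scales**

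The documents give no correlations, so those below are assumptions on the severity scale (multivariate normal, 2,000,000 simulated patients; the first row is the exact result). Arrows run from as written to reversed; DM is diffuse malignant.

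| Part II–III / other scales / cognition with the rest | Change class | DM in best cognitive quarter | DM in worst quarter | Mild in worst quarter |
|---|---|---|---|---|
| 0 / 0 / 0 | 29.9% | 47.3% → 19.1% | 19.1% → 47.3% | 31.6% → 0% |
| 0.4 / 0.2 / 0.1 | 30.9% | 36.8% → 15.7% | 25.2% → 48.9% | 33.0% → 0% |
| 0.5 / 0.3 / 0.2 | 31.3% | 29.7% → 12.3% | 31.0% → 53.2% | 30.3% → 0% |
| 0.6 / 0.4 / 0.3 | 31.7% | 23.5% → 9.4% | 36.7% → 57.2% | 27.8% → 0% |

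With one common correlation from 0 to 0.4 (1,000,000 patients), 29.9 to 31.1% change class. Of those labelled diffuse malignant, 12 to 27% are not; 19 to 27% of the correctly defined group are missed; and 19 to 33% of the mild group are in the worst cognitive quarter.

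**Would group sizes reveal it?** Hardly. In the table's scenarios diffuse malignant is 25 to 26% as written and 26 to 27% reversed, and every group passes the SAP's 20% threshold for running a subgroup either way.

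**The case against.** Several points can fairly be made on the other side.

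- **Reach.** This is one of six main-body subgroups, reported with 80% intervals in a study without multiplicity adjustment. The primary model, its covariates, the alpha level and the sample size do not use it. That is correct.
- **The extremes never swap.** Under either orientation diffuse malignant needs a high motor score, or SCOPA-AUT and RBDSQ both high, and each of these bars mild under either orientation. Every change is into or out of intermediate. This stands, and the contrast between the extreme groups is hurt less than a 30% figure suggests.
- **High MoCA alone is not enough.** It acts only together with other scores. In the most correlated row above, the best cognitive quarter is labelled diffuse malignant slightly less often than all patients (23.5% against 25.1%). Even so, that is two and a half times the 9.4% obtained with MoCA reversed.
- **The figures assume continuous scales.** With integer scores, ties and a capped MoCA, under assumed score distributions, reclassification ran from about 20% to 39%, and in some cases the diffuse malignant or mild group fell below the 20% threshold. The size is therefore uncertain; the direction is not.
- **Phase 3 use.** No passage says Phase 3 would enrich on this sub-phenotype. The SAP says only that main-body analyses inform its design.
- **Intent.** MoCA's direction is inferred from the comparison with the MMSE, and the authors may have meant severity-ordered percentiles. The text does not say so, and a programmer following it would rank the raw MoCA score.

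**Conclusion.** The concern holds. SAP 4.7.5 and protocol 6.6 put MoCA into the rule with the wrong sign, and nothing elsewhere in either document corrects it. This is a wrong definition rather than a missing detail, because following it exactly gives the wrong classes.

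About three patients in ten change class under continuous scales, and roughly 20 to 39% with integer scores. These figures rest on assumed correlations and score distributions. The logical consequences need no assumption beyond MoCA's direction: best-quartile cognition can never be mild, and worst-quartile cognition can be. The damage is confined to the sub-phenotype analyses, but those cover the primary endpoint and most of the key secondary ones. It should be corrected before they are run.

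**What to change.** In SAP 4.7.5, state that MoCA is reversed before the rule is applied. A MoCA below its 25th percentile counts as a severe non-motor score in both diffuse malignant routes, and mild motor-predominant requires a MoCA above its 25th percentile. Equivalently, define all percentiles in the direction of greater severity and use the maximum score minus MoCA. State the direction of RBDSQ in the same sentence, and apply the 20% threshold to the corrected groups.

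The SAP edit is the operative one, since SAP section 1 gives it precedence over the protocol's analysis plan. Protocol 6.6 can be aligned at the next amendment and does not need one of its own.

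The cost is one sentence and one line of derivation code, with no effect on patients, data collection or the primary analysis. It is best done before unblinding. If treatment codes are already open, report it as a correction and show both versions.
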